2.1.2. Endpoints

Primary Endpoints

- AEs throughout the study
 - Local and systemic solicited AEs for 7 days post-vaccination.
 - AEs for 28 days after each vaccination.
 - Discontinuations from vaccination/from study due to AEs.
 - SAEs and AEs of special interest (AESIs) during the course of the study, including the optional LTE phase.
- Env-specific binding Abs (titers and breadth).

Secondary Endpoints

- Env-specific nAbs (titers and breadth) (for Tier 1 and Tier 2 viruses; note: Tier 2 will be assessed only if Tier 1 shows positive results).
- Env-specific functional Abs (phagocytosis score and breadth).
- Env-specific binding Ab isotypes (IgA, IgG1-4) (titers and breadth).
- IFN γ PBMC responders to mosaic peptide pools of Env/Gag/Pol and PTE.
- CD4 $^{+}$ and CD8 $^{+}$ T-cell functionality (% cells producing ia, IFN γ , IL-2, IL-4, TNF α).
- T-cell development with emphasis on follicular helper T-cells and memory differentiation.
- Available samples from time points after last vaccination until the final main study visit at Week 72 will be used for determination of durability of the immune responses.

Exploratory Endpoints

- Ab functionality evaluation (by other than phagocytosis).

- Ab Fc (sub)typing.
- Epitope mapping of Ab to Env and T-cell responses to Gag/Pol/Env and PTE.
- Regulation of genes (clusters) that predict specific immune responses and human leukocyte antigen (HLA) typing.
- Ab-producing B-cells and characterization of B-cell memory development.
- Ad26 nAbs (titer).
- Available samples from time points during the optional LTE phase will be used for determination of long-term durability of the immune responses.

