9.1.4. Vaccination

Visit 2/Randomization/Vaccination 1

After re-check of inclusion/exclusion criteria (including concomitant medication), abbreviated physical examination (including weight measurement), measurement of vital signs, and a urine pregnancy test (for women of childbearing potential), eligible subjects will be randomized as described in Section 5.

If medical status and/or physical examination suggest(s) significant changes have occurred since screening, the clinically relevant screening assessments will be repeated and the Day 1 visit rescheduled. If the repeat screening assessment causes the subject to fall outside the screening window, all screening safety procedures should be repeated so that they are not more than 28 days prior to the Day 1 visit. These subjects will not be considered screen failures, if their repeat labs meet the inclusion criteria.

Pre-dose samples for hematology, biochemistry, HIV testing, urinalysis, and immunogenicity will be collected. Human leukocyte antigen will also be tested using the baseline blood sample. Pre-dose AEs will also be collected, together with information about any concomitant medications.

Study vaccine will be prepared by the site pharmacist, who will place an overlay on the syringes (to preserve blinding) and will send it to the clinic. After each vaccination, subjects will remain under observation at the study site for at least 30 minutes for presence of any acute reactions and solicited local (at injection site) and systemic events (see Section 9.3), and vital signs measurement will be repeated.

Subjects will be provided with a thermometer, ruler, and subject diary to measure and record body temperature and solicited local (at injection site) and systemic events for 7 days post-vaccination (day of vaccination and the subsequent 7 days).

In addition to an HIV-risk assessment, counseling related to avoidance of HIV infection, pre- and post-HIV-test counseling, and pregnancy counseling will be provided to all subjects (men and women).

Visit 6/Vaccination 2

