9.3. Safety Evaluations

Details regarding the PSRT and DRC are provided in Section [11.7](#) and [11.8](#), respectively.

Any clinically relevant changes occurring during the study must be recorded on the AE section of the CRF.

Any clinically significant abnormalities persisting at the end of the study/early withdrawal will be followed by the investigator until resolution or until a clinically stable endpoint is reached.

The study will include the following evaluations of safety and tolerability according to the time points provided in the [Time and Events Schedule](#):

AEs

All AEs will be reported from the time a signed and dated ICF is obtained until 28 days after first dose of study vaccine, and thereafter, pre-dose and for 28 days after each subsequent dose of study vaccine/placebo. Unsolicited AEs with the onset date outside the timeframe defined above (>28 days after previous study vaccination), which are ongoing on the day of the subsequent vaccination, should be recorded on the CRF AE page. All SAEs and AEs leading to discontinuation from the study vaccination and AESIs (ie, confirmed HIV infection) are to be reported for the duration of the main study (see Section [12.3.1](#) for details). During the optional LTE phase, only SAEs and AESIs are to be reported. Other AEs are not collected during the optional LTE phase as the optional LTE phase begins 6 months after the last vaccination and it is very unlikely that an AE related to the study vaccine would only present that long after the last vaccination.

Adverse events will be followed by the investigator as specified in Section [12](#).

For solicited AEs, the following applies.

Solicited AEs

After vaccination, subjects will remain under observation at the study site for at least 30 minutes for presence of any acute reactions and solicited events. In addition, subjects will record solicited events in a diary for 7 days post-vaccination. All subjects will be provided with a diary and instructions on how to complete the diary (Section [9.1.1](#)). Diary information will be transcribed by the study personnel in the appropriate CRF pages.

Injection Site (Local) AEs

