### **5. SAFETY**

The safety and tolerability endpoints are:

- Unsolicited AEs 28 days following each vaccination
- Solicited local and systemic AEs (reactogenicity), collected daily from day of vaccination for 7 days post-vaccination (day of vaccination and the subsequent 7 days).

The safety and tolerability analysis will be performed on the FA set. Specifically, the analysis for solicited adverse events will be done on those subjects in the FA set for whom reactogenicity assessments are available in the database (either via on-site assessments or via the diary pages of the CRF).

Safety data will be tabulated per period by regimen. Only the active periods will be shown in the tables (AE, Lab, VS), except for SAEs. In addition, for a selection of tables (AE, Lab), tabulations per subject by vaccine and per dose by vaccine will be provided.

In the ‘per subject by vaccine’ analysis, the safety will be presented per periods (post-dose 1, 2, 3, 4) by vaccine rather than by regimen. A ‘post any dose’ period (= regimen phase in section 2.1) will be added, that summarizes the safety after all administered doses of a vaccine. The post-any-dose period allows determining how many subjects reported events after administration of a certain vaccine regardless the number of doses. Each subject is counted only once. In case a subject has the same event after more than one dose, it is counted only once (and in case of showing attributes,

the worst corresponding attribute is shown) in the post-any dose period. The denominator is the number of subjects that received the considered vaccine in the considered period.

In the ‘per dose by vaccine’ analysis, the safety will also be presented by vaccine. This table allows determining the incidence of events per administered dose of a certain vaccine. For example, if a subject has the same event at least once after dose 1 and at least once after dose 2 of the same vaccine, it is counted 2 times (so the numerator is the sum of post-dose 1, 2, 3 and 4 events in the “per subject by vaccine” table). In case of showing attributes, the worst corresponding attribute of each period are shown. The denominator is the total number of doses administered of the considered vaccine over all subjects.

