### **5.1.1. Definitions**

Solicited AEs shown in the tables are extracted from the diary pages of the CRF. For unsolicited AEs, only the AEs within the 28-day period following each vaccination will be presented in the safety tables except for SAE and AESI (AE of special interest), which will be captured and tabulated in the outputs covering the whole study period. All other collected unsolicited adverse events will be presented through listings.

Solicited local AEs will be by definition considered as related to the study vaccine.

The severity of the AEs will be classified as grade 1 to 4. Solicited events that are graded less than grade 1, are not considered as AE. In case no grades are available, the grading of the solicited events will occur according to the grading list in attachment 1 of the CTP.

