#### **5.1.4. Handling of Missing Data for Adverse Events**

Missing data will not be imputed. Subjects who do not report an event will be considered as subjects without an event. The analysis of the solicited AEs will include only documented safety data (i.e. in case severity is missing it is not considered an event).

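### Solicited-AE denominators admit subjects with only the on-site check, so any missing diary lowers the primary 7-day rates

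*SAP*

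**What the plan says.** Protocol 2.1.2 lists "Local and systemic solicited AEs for 7 days post-vaccination" among the primary endpoints. SAP 5 defines the window as vaccination day plus seven days.

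For the denominator, SAP 5 takes subjects in the Full Analysis Set "for whom reactogenicity assessments are available in the database (either via on-site assessments or via the diary pages of the CRF". Under Protocol 9.3, after vaccination "subjects will remain under observation at the study site for at least 30 minutes for presence of any acute reactions and solicited events"; Protocol 9.1.4 repeats this for each vaccination visit. For the by-vaccine tables SAP 5 says: "The denominator is the number of subjects that received the considered vaccine in the considered period". The per-dose version divides by all doses given.

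For the numerator, SAP 5.1.1 says: "Solicited AEs shown in the tables are extracted from the diary pages of the CRF". SAP 5.1.3, which builds the solicited-AE dataset, keeps an on-site assessment as its own record when it differs from the diary entry for the same day. Its worked example stores an on-site headache beside the diary records.

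For missing data, SAP 5.1.3 analyses a day without data as a day without an event. SAP 5.1.4 adds: "Subjects who do not report an event will be considered as subjects without an event".

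**The concern.** Each rule is unremarkable alone. The difficulty is the combination. The on-site check is planned for every subject at every dose, so the either/or condition lets in nearly every vaccinated subject, with or without a diary. Events come mainly or only from the diary, and silence is read as absence. A subject who returns no diary after a dose is counted as free of reactions over eight calendar days on the strength of about half an hour's observation. Partly completed diaries are affected in the same way, day by day.

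At stake is a descriptive primary safety result for a first-in-human vaccine. The SAP plans no diary-completeness table, no minimum number of diary days and no sensitivity analysis, so a reader of the report could not tell whether the effect was nil or material. SAP 5.2.1 already uses a better rule for laboratory data: percentages are taken over subjects with non-missing data for the parameter, period and group.

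**Working it through.** **Inputs from the documents.** The denominator is on-site or diary (SAP 5), and the on-site check is planned for all (Protocol 9.1.4, 9.3). Events come from the diary (SAP 5.1.1), possibly with differing on-site records (SAP 5.1.3). Missing counts as no event (SAP 5.1.3, 5.1.4). Planned group 2A size is 110.

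**Inputs not in the documents, assumed here.**
- m, the share of doses with no diary: 2%, 5%, 10%.
- c, the share of those subjects' reactions caught on site and counted: 0 (diary-only reading of SAP 5.1.1) or 0.25 (on-site records counted).
- p, the true 7-day rate: 50% or 80%.

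The plan states no solicited-AE rate and no diary-return rate, so there is no figure of its own to reproduce. The zero-event bounds in Protocol 11.3 concern AEs that would preclude further vaccination, and they do not bear on this point.

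**Formula.** Write p_D and p_N for the true rates in subjects with and without a diary.
- True rate = (1 − m) × p_D + m × p_N
- Tabulated rate = (1 − m) × p_D + m × c × p_N
- Shortfall = m × (1 − c) × p_N

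If p_N = p_D = p, the tabulated rate is p × [(1 − m) + m × c], a relative understatement of m × (1 − c).

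| m | p = 50%, c = 0 | p = 50%, c = 0.25 | p = 80%, c = 0 | p = 80%, c = 0.25 |
|---|---|---|---|---|
| 0% | 50.0% | 50.0% | 80.0% | 80.0% |
| 2% | 49.0% | 49.25% | 78.4% | 78.8% |
| 5% | 47.5% | 48.1% | 76.0% | 77.0% |
| 10% | 45.0% | 46.25% | 72.0% | 74.0% |

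In counts, with 110 vaccinated and 11 diaries absent (m = 10%, c = 0, p = 50%), 99 × 0.50 = 49.5 reactors are tabulated, and 49.5/110 = 45.0%. Dividing by the 99 subjects with diaries gives 50.0%.

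**Sensitivity to the equal-rate assumption** (m = 10%, c = 0, p_D = 50%). The tabulated rate is 45.0% throughout.
- p_N = 50%: the true rate is 50.0%.
- p_N = 25%: the true rate is 0.9 × 50 + 0.1 × 25 = 47.5%.
- p_N = 0: the true rate is 45.0%. The tabulated rate is then correct, and the diary-only rate of 50.0% is too high.

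So the shortfall is never negative, but its size depends on p_N.

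**The case against.** The strongest reply is that no bias has been shown. The protocol works to keep diaries complete: subject training (9.1.1), contact at 24 to 72 hours and staff review of the diary at the two-week visit (9.1.5), and transcription by study personnel (9.3). The missing share may be negligible. This stands: m is unknown and could be zero.

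Second, SAP 5.1.3 keeps on-site records, so events do not come from diaries alone. This stands in part. It conflicts with SAP 5.1.1, and the 5.1.3 rule is framed as a difference from a diary entry, so it does not say what happens when there is no diary. Counting on-site events shrinks the shortfall but removes it only if every reaction is caught in that first observation. Anyone taking p × (1 − m) as the size of the effect would be quoting the worst case, c = 0.

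Third, subjects who return no diary may have had nothing to report. This stands, and it is why both denominators should be shown.

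Fourth, SAP 5.1.4 restricts the analysis to documented data. That does not help: its own explanation is that events with missing severity are dropped, which lowers the numerator and leaves the denominator alone.

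Two stronger readings are tempting. A reader might infer that one assessment at any dose qualifies a subject for all doses. SAP 5 does not say so; it tabulates by period and leaves open whether the availability condition applies per period. A reader might also infer that doses 3 and 4 would look better tolerated than doses 1 and 2. That needs diary return to fall over time, and nothing in the documents suggests it.

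**Conclusion.** The concern holds as a conditional one. As written, a subject with no diary for a dose enters a primary 7-day rate as event-free. If any diaries are missing, the rates are understated by a relative m × (1 − c), assuming subjects without diaries react at the same rate as the others. For m between 2% and 10% with c = 0, a true 50% shows as 49.0% to 45.0%. The loss is smaller if on-site records count, and nil if diaries are complete or non-returners truly had no reactions. The values of m, c and p are all assumptions. The documents do not support saying that the rates are in fact biased, or by how much. They do support saying that the all-vaccinated rate is the lowest answer consistent with the collected data, and that the plan gives readers no means of judging the gap. Safety is descriptive with no formal testing, so no test result is affected. A comparison with placebo would be distorted further only if diary return differed between groups.

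**What to change.** SAP 1 states that the Week 72 analysis has been performed and will not be rerun, and the extension phase has no vaccinations. Editing SAP 5 and 5.1.4 alone would therefore change no table still to come. Provide a supplementary table in the final report instead:

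- For each post-dose period, give solicited-AE rates with, as denominator, subjects vaccinated at that dose who have diary data for that period, and show n. State a minimum number of diary days for the main version: a one-day minimum would still leave the other days counted as event-free under SAP 5.1.3.
- Place these beside the all-vaccinated rates, labelled as the lower-bound assumption that absent diaries mean no reaction. The diary-based rate is not an upper bound, since non-returners could react more often.
- Report subjects with only an on-site assessment separately.
- Tabulate absent and partial diaries by group and dose.
- Reconcile SAP 5.1.1 with 5.1.3, and state whether on-site events were counted in the tables, including when no diary exists.

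The cost is a denominator flag, one extra table and slightly smaller denominators. If diaries were complete, the table shows it and the matter is closed.

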An abbreviated physical examination (including weight measurement) and measurement of vital signs, will be performed for all subjects pre-vaccination. A urine pregnancy test must be performed before vaccination for women of childbearing potential, and results must be available and negative prior to vaccination. Pre-dose samples for hematology, biochemistry, HIV testing, and urinalysis will be collected. A pre-dose blood sample for the immunogenicity assays will be drawn. Pre-dose AEs will also be collected, together with information about any concomitant medications. After each vaccination, subjects will remain under observation at the study site for at least 30 minutes for presence of any acute reactions and solicited local (at injection site) and systemic events (see Section 9.3), and vital signs measurement will be repeated.

Subjects will be provided with a thermometer, ruler, and subject diary to measure and record body temperature and solicited local (at injection site) and systemic events for 7 days post-vaccination (day of vaccination and the subsequent 7 days).

In addition to an HIV-risk assessment, counseling related to avoidance of HIV infection, pre- and post-HIV-test counseling, and pregnancy counseling will be provided to all subjects (men and women).

Subjects will complete a social impact questionnaire ([Attachment 4](#)).

Visit 9/Vaccination 3

The procedures for Visit 9 will be the same as at Visit 6 as detailed above, with the exception of the social impact questionnaire which will not be completed.

Visit 13/Vaccination 4

The procedures for Visit 13 will be the same as at Visit 6 as detailed above.

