9.1.6. Follow-Up Phase

Follow-up visits will be performed at the clinic at Week 60 and 72. Each visit includes a vital signs measurement, recording of concomitant medications, recording of SAEs, AEs leading to treatment discontinuation, and AESIs, and collection of samples for immunogenicity and safety laboratory testing (CBC and serum chemistry). In addition to an HIV-risk assessment, counseling related to avoidance of HIV infection will be provided to all subjects.

A complete physical exam will be performed at the final main study visit (Week 72). At Week 60, an abbreviated, symptom-directed exam will be performed as indicated by the investigator. Weight will be measured at both visits.

At the final main study visit (Week 72), samples for HIV testing and urinalysis will be collected. Pre- and post-HIV-test counseling will be provided to all subjects. Subjects will also complete a social impact questionnaire ([Attachment 4](#)).

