**Table 3: Phase and Period Definitions**

Phase	Phase number	Period	Period number	Interval	
				From	To
Follow-Up 1	3			1 minute after end of Post-Dose 1 period	Minimum of: a) One minute prior to date and time of the next vaccination b) 23:59 at the date of last contact (for early discontinuation)
Regimen	2	Post-Dose 2	2	Date and time of Dose 2 (Day 85)	Minimum of: a) Maximum (28 days after second vaccination at 23:59, scheduled visit 4 weeks after second vaccination at 23:59) b) 23:59 at the date of last contact (for early discontinuation) c) One minute prior to post-dose 3
Follow-Up 2	4			1 minute after end of Post-Dose 2 period	Minimum of: a) One minute prior to date and time of the next vaccination b) 23:59 at the date of last contact (for early discontinuation)
Regimen	2	Post-Dose 3	3	Minimum of Date and Time of the two Dose 3 Injections (Day 169)	Minimum of: a) Maximum (28 days after the third vaccination at 23:59, scheduled visit 4 weeks after third vaccination at 23:59) b) 23:59 at the date of last contact (for early discontinuation)
Follow-Up 3	5			1 minute after end of Post-Dose 3 period	Minimum of: a) One minute prior to date and time of the next vaccination b) 23:59 at the date of database cut-off c in case of interim c) 23:59 at the date of last contact (for early discontinuation)
Regimen	2	Post-Dose 4	4	Minimum of Date and Time of the two Dose 4 Injections (Day 337)	Minimum of: a) Maximum (28 days after fourth vaccination at 23:59, scheduled visit 4 weeks after fourth vaccination at 23:59) b) 23:59 at the date of database cut-off c in case of interim c) 23:59 at the date of last contact (for early discontinuation)
Follow-Up 4	6			1 minute after end of Post-Dose 4 period	Minimum of: a) Last available visit for completers b) 23:59 at the date of last contact (for early discontinuation) c

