**NOTE:**

a The start time of screening phase is 00:00. In case an earlier date is available (e.g. for lab or vital signs then use the very first date in order to include all data)

b In case a dose is not administered, the observations end up in the previous Follow-Up phase

c This timepoint is intended to be at the end of the main study i.e. Week 72. LTE data will be reported separately

For the immunogenicity analyses no phases will be constructed.

The periods/phases will be used primarily for safety and concomitant medication allocation. The post-dose periods (and the regimen phase) are considered active periods/phase, the screening and follow-up phases are considered non-active phases. There will be no phase defined for the LTE part of the study.

For descriptive statistics over time, assessments (regardless of the investigated parameter) will be allocated to an analysis visit based on the visit number as captured in the database.

For subjects that received a first dose, but did not receive a 2nd dose while still continuing their planned visit schedule, the measurements after the planned but not administered 2nd dose will not be included in graphs and tables showing descriptive statistics over time. Those measurements will be shown in listings but it will be indicated that these are not used in the analysis. Moreover, the vaccinations done after a missed one will not be shifted to the previous one but will be considered as planned: in the example above if the 2nd is missed, the 3rd vaccination will still be reported as post-dose 3.

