### 5.2.1. Analysis methodology

Laboratory data will be analyzed based on the full analysis set. Unless specified otherwise, percentages are calculated versus the number of subjects in the analysis set with non-missing data for the parameter, period (if applicable) and treatment group under evaluation.

Tabulations of the worst graded abnormalities per period following vaccination will be provided. Grade 3 and 4 toxicities developed following vaccination will be listed. Tabulations of the worst emerging abnormalities (below/ above) will be performed for tests that have no grading.

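### The active-period display rule keeps 6 of 10 scheduled post-baseline safety-laboratory draws and all 4 scheduled post-baseline urinalyses out of the laboratory tables

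*SAP*

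**What the plan says.** The display rule is in SAP section 5: "Only the active periods will be shown in the tables (AE, Lab, VS), except for SAEs". The only exception is for serious adverse events.

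SAP 2.1 defines the terms: "The post-dose periods (and the regimen phase) are considered active periods/phase, the screening and follow-up phases are considered non-active phases". Table 3 there starts each post-dose period at the date and time of the dose. It ends the period at the later of 28 days and the scheduled 4-week visit, or at last contact if that is earlier. Follow-Up phases 1 to 3 each run until "One minute prior to date and time of the next vaccination"; Follow-Up 4 runs to the end of the main study.

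SAP 5.2 determines worst laboratory grades separately for each trial phase. SAP 5.2.1 plans tables of worst grade per period following vaccination, with subjects having non-missing data as the denominator. It adds a listing: "Grade 3 and 4 toxicities developed following vaccination will be listed". Appendix 1 gives grades for hematuria and proteinuria.

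On sampling, Protocol 9.1.4 says of Visit 6 (Week 12), and by reference of Visits 9 and 13 (Weeks 24 and 48): "Pre-dose samples for hematology, biochemistry, HIV testing, and urinalysis will be collected". Protocol 9.1.6 says: "At the final main study visit (Week 72), samples for HIV testing and urinalysis will be collected". Protocol 11.5 promises laboratory abnormalities by treatment group and/or vaccine; the 28-day limit in that section is written for adverse events only.

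**The concern.** The tabulation rule and the sampling schedule do not fit together. Active periods begin at the dose, but at Weeks 12, 24 and 48 the laboratory samples are taken before the dose, so they belong to the preceding follow-up phase. Weeks 36, 60 and 72 lie well after the 28-day windows. Urinalysis is affected most: after baseline it is scheduled only before a dose or at Week 72, apart from early exit, so the graded urinalysis parameters have no scheduled sample to tabulate.

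At stake is the comparison with placebo. This is the first-in-human study of Ad26.Mos4.HIV, and Protocol 3.2 gives the placebo arm the task of showing how often changes occur without active treatment. For mild or moderate laboratory changes that first appear, or are still present, outside the 28-day windows, the planned tables give no rate in any arm.

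**Working it through.** Neither document states a figure on this point, so there is none to reproduce. The check is a count.

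**Inputs.** Scheduled post-baseline CBC/chemistry and urinalysis come from the text of Protocol 9.1.4 to 9.1.6, visit windows from Protocol 9.1.2, and periods from SAP Table 3. Protocol 9.5 requires sample times to be recorded, so a pre-dose sample can be separated from the dose given the same day.

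**Allocation at nominal days.**

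| Week (visit) | Safety samples | Phase or period | In tables? |
|---|---|---|---|
| 2 (4) | blood | Post-Dose 1 | yes |
| 12 (6), pre-dose | blood, urine | Follow-Up 1 | no |
| 14 (7) | blood | Post-Dose 2 | yes |
| 24 (9), pre-dose | blood, urine | Follow-Up 2 | no |
| 26 (10) | blood | Post-Dose 3 | yes |
| 36 (12) | blood | Follow-Up 3 | no |
| 48 (13), pre-dose | blood, urine | Follow-Up 3 | no |
| 50 (14) | blood | Post-Dose 4 | yes |
| 60 (16) | blood | Follow-Up 4 | no |
| 72 (17) | blood, urine | Follow-Up 4 | no |

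Blood: 4 of 10 draws tabulated, 6 of 10 not. Urinalysis: 0 of 4 tabulated.

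**Do visit windows change the count?** The latest end of a post-dose period is the latest allowed dose day + 28 + 5, the 5 being the upper window of the 4-week visit.

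- Two-week draws: 14 ± 5 = 9 to 19 days after the dose, always inside 28 days.
- Week 36: earliest day 253 − 5 = 248; latest end of Post-Dose 3 is 169 + 21 + 28 + 5 = 223. Outside by 25 days.
- Week 60: earliest day 421 − 21 = 400; latest end of Post-Dose 4 is 337 + 21 + 28 + 5 = 391. Outside by 9 days.
- Week 72: earliest day 505 − 21 = 484, also after 391.
- Pre-dose samples at Weeks 12, 24 and 48 precede their own dose. The earliest days for those visits (78, 162 and 330) come after the latest ends of the preceding post-dose periods (1 + 28 + 5 = 34; 85 + 21 + 28 + 5 = 139; and 223).

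The 4/6 and 0/4 splits hold at every combination of window limits.

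**Does another planned table pick these samples up?** The post-any-dose column in the by-vaccine tables is defined as the regimen phase, so it contains only the four post-dose periods. A skipped dose does not help either: under the Table 3 notes its observations stay in the previous Follow-Up phase.

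**The case against.** The strongest reply is that the SAP does not clearly intend the exclusion. SAP 5.2 derives worst grades for each phase, and the phases include Follow-Up 1 to 4. SAP 5.2.1 computes percentages by period only if applicable. SAP 2.1 allocates all assessments to visits for descriptive statistics over time. These passages show that follow-up grades will exist in the data. None sets up a laboratory table showing them, and the section 5 rule names laboratory tables expressly. The passages conflict and need reconciling, but they do not remove the gap.

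A second reply is that dose-linked windows are a reasonable choice: they match the 28-day adverse-event endpoint, and laboratory values are not a named primary endpoint. That justifies keeping the per-period columns. It does not justify having no rates from the other samples, which Protocol 11.5 treats without a 28-day limit.

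A third reply concerns safeguards, and much of it stands. A reader might infer that abnormalities outside the windows become invisible. The documents do not support that. Grade 3 and 4 toxicities after vaccination are listed without an active-period limit. Clinically relevant values are to be recorded as adverse events. Protocol 9.3 calls for confirmatory and repeat testing of Grade 3, Grade 4 or symptomatic abnormalities. An abnormality already present at a 2-week post-dose draw is tabulated there; only its persistence is not. The adverse-event route is weaker late on: the procedures for Weeks 36, 60 and 72 mention only serious events, events leading to treatment discontinuation and events of special interest, and SAP 5.1.1 puts other unsolicited events outside 28 days in listings only.

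**Conclusion.** The point holds for tables. As written, 6 of 10 scheduled post-baseline CBC/chemistry draws and all 4 scheduled post-baseline urinalyses are not shown in the laboratory tables. What is lost is by-arm rates, mainly of Grade 1-2 abnormalities first seen or persisting outside the 28-day windows, and all urinalysis rates from scheduled samples. It is a reporting gap that should be closed; the data are collected and graded.

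Two further readings go too far. The count does not cover all blood draws: draws for immunogenicity alone, at Weeks 4, 16, 28 and 52, are outside it. Nor must the urinalysis tables be completely empty, since an unscheduled sample or an early-exit visit inside a post-dose period could still enter them.

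The count assumes that sample clock times are used for allocation and that doses fall within their windows. After a study pause a later dose is possible. A Week 60 draw on Day 400 could fall in Post-Dose 4 only if the fourth dose came on Day 400 − 33 = 367 or later, against a latest allowed Day 337 + 21 = 358.

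**What to change.** Exempt laboratory data from the active-period-only rule in SAP section 5, and say in 5.2.1 how the phase-level grades of 5.2 are shown. Add a column giving the worst emergent grade at any time post-baseline to Week 72, by regimen, over all scheduled and unscheduled samples and including urinalysis. Keep the per-period columns.

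Timing limits the form. SAP section 1 says the Week 72 analysis has been done and will not be rerun, and the extension schedule has no CBC, chemistry or urinalysis. The column should therefore be a supplementary table in the final report, labelled as added after unblinding. If an equivalent table was already produced at Week 72, the SAP need only say so.

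The cost is one supplementary output from existing data. The downside is small: late values are less specific to a dose, which is why the per-period columns stay.
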